2.1.2 Secondary Objectives

The secondary objectives are:

- To compare the efficacy of AM0010 in combination with FOLFOX versus FOLFOX alone in patients with metastatic pancreatic cancer as measured by:
 - PFS
 - Objective response rate (ORR), DCR, and duration of response (DoR) by Response Evaluation Criteria in Solid Tumors (RECIST) v.1.1
 - 1-year survival rate
- To compare the safety and tolerability of AM0010 in combination with FOLFOX versus FOLFOX alone

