2.2.1 Treatment Duration

Each cycle is 14 days, with Days 6, 7, 13, and 14 being rest days for AM0010. FOLFOX will be administered on Day 1 of each cycle. Patients randomized to the investigational combination treatment (AM0010 plus FOLFOX) ARM 1, after completion of up to 12 cycles of combination chemotherapy or if experiencing chemotherapy intolerance (as defined as Grade 3 or 4 non-hematologic toxicity that has not resolved to baseline in 28 days or Grade 4 hematologic toxicity that has not resolved to baseline in 28 days) may continue to receive maintenance AM0010 if the patient continues to receive clinical benefit (CR, PR, or SD). Patients may receive FOLFOX on both study arms for up to 12 cycles or 24 weeks. Patients will be treated until tumor progression by RECIST v.1.1.

Patients may continue on treatment until they experience progressive disease, unacceptable toxicity, require palliative radiotherapy, withdraw consent, or their physician feels it is no longer in their best interest to continue on study treatments.

To mitigate the chance of detecting false-progression (ie, pseudoprogression) early in the course of treatment on ARM 1 with AM0010 in combination with FOLFOX, patients whose scans show radiographic progression in the absence of clinical deterioration including worsening ECOG PS as assessed by the Investigator may remain on study treatments and should have an additional scan 4

weeks (± 3 days) later as outlined in Section 8.1.1. If this subsequent scan shows disease progression, the patient will be discontinued from study treatments.

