6.4. Treatment Duration

Each cycle is 14 days, with Days 6, 7, 13, and 14 being rest days for pegilodecakin. FOLFOX will be administered on Day 1 of each cycle. Patients randomized to the investigational combination treatment (pegilodecakin plus FOLFOX) ARM 1, after completion of up to 12 cycles of combination chemotherapy or if experiencing chemotherapy intolerance (as defined as Grade 3 or 4 non-hematologic toxicity that has not resolved to baseline in 28 days or Grade 4 hematologic toxicity that has not resolved to baseline in 28 days) may continue to receive maintenance pegilodecakin if the patient continues to receive clinical benefit (CR, PR, or stable disease [SD]). Patients will be treated until tumor progression by RECIST v.1.1. For ARM 2 (FOLFOX only) patients may receive FOLFOX for up to 12 cycles or 24 weeks or until tumor progression by RECISIT v.1.1 or until patients experience unacceptable toxicity, require palliative radiotherapy, withdraw consent, or their physician feels it is no longer in their best interest to continue on study treatments whichever occurs earlier.

To mitigate the chance of detecting false-progression (ie, pseudoprogression) early in the course of treatment on ARM 1 with pegilodecakin in combination with FOLFOX, patients whose scans show radiographic progression in the absence of clinical deterioration including worsening Eastern Cooperative Oncology Group (ECOG) Performance Status (PS) as assessed by the Investigator may remain on study treatments and should have an additional scan 4 weeks (±3 days) later as outlined in protocol Section 8.1.1. If this subsequent scan shows disease progression, the patient will be discontinued from study treatments.

7. General Statistical Considerations

7.1. Population:

The enrolled population includes all patients who sign the informed consent document.

The intent-to-treat (ITT) population includes all randomized patients per interactive voice response system (IVRS).

The safety population includes all randomized patients who received any amount of pegilodecakin or FOLFOX.

Per-Protocol Population: All patients who are in the safety population and have no major protocol deviations.

The major protocol deviations which will result in exclusion from the Per-Protocol population are listed below. This is not an exhausted list and may be amended over the course of the trial.

- patients with disease other than metastatic pancreatic adenocarcinoma
- patients with ECOG >1 at baseline

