10.1.1. Treatment Exposure

The following parameters will be summarized by treatment arm:

Overall Treatment:

- duration of treatment (months):
 - \circ Pegilodecakin: (last dose date first dose date+1)/ 30.4375
 - Any component of FOLFOX: (last dose date first dose date + 14)/30.4375
- number of cycles administered (patient with total number of cycles administered, 1 cycle, 2 cycles, 3 cycles, etc.)
- total number of cycles administered

The following parameters will be summarized (descriptive statistics) by study drug component within each treatment arm:

- total cumulative dose (mg for pegilodecakin and mg/m² for each FOLFOX drug component)
- total dose per cycle (dose intensity)
- relative dose intensity (%), summarized by descriptive statistics and by categories of [60%, 80%), [80%, 100%), [100%, 120%) and ≥120%, etc.

In ARM 1(Pegilodecakin + FOLFOX), pegilodecakin's will be treated up to 12 cycles with 4 mg/cycle (2weeks) for patients with weight \leq 80 kg and 8 mg/cycle (2weeks) for patients with weight >80 kg. After the 12 cycle, patient receiving benefit on ARM 1 can continue on maintenance cycle with double of the dose 8 mg/2 weeks for patients with weight \leq 80 kg and 16 mg/2 weeks for patients with weight >80 kg. Therefore the exposure will be summarized in the following categories:

- for FOLFOX, exposure will only be summarized up to 12 cycles.
- for Pegilodecakin:
 - Cumulative dose, total dose per cycle and relative dose intensity will be summarized up to 12 cycle prior to maintenance period and repeated within the maintenance period.
 - The duration of treatment, and number of cycle administered will be summarized across all treatment durations and repeated for the maintenance cycle.

The key parameters used to calculate dosing data are shown in Table JZGB.10.1:

Table JZGB.10.1.	Patient Exposure Prior to Maintenance Period
------------------	--

		FOLFOX		
Treatment	pegilodecakin	Oxaliplatin	Leucovorin	5- FU
Planned Dose intensity	4 mg/cycle (14 days) (≤ 80kg) 8 mg/cycle (14 days) (> 80kg)	85 mg/m ² per cycle(14 days)	400 mg/m ² per cycle (14 days)	2800 mg/m ² per cycle (14 days)
Cumulative dose	sum of the doses mg for pegilodecakin, or mg/m^2 for FOLFOX administered to a patient during the treatment period			
Actual Dose intensity	Cumulative dose/ duration of treatment (mg/2week)	ration of treatment (mg/m ² /cycle)		
Relative dose intensity (%)	Actual Dose intensity/planned dose intensity			

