12.1. Adverse Events

Adverse event terms will be coded using the latest version of MedDRA (version 19.0 or later). Adverse events (AEs) will be graded according to the National Cancer Institute (NCI) Common Terminology Criteria for Adverse Events (CTCAE) v4.03.

Summaries of AEs will be generated for those events that are considered treatment emergent, where a TEAE is defined as an AE that begins or worsens in grade after the date of first study drug administration through 30 days after all treatment discontinuation. Any related serious adverse event (SAE) which occurs more than 30 days after all treatment discontinuation will also be considered as TEAE.

All AE data will be presented in listings; separate listings for serious AEs, AEs leading to any study treatment discontinuation (either FOLFOX or Pegilodecakin), and AEs leading to death will be generated. Adverse events by subgroup (age, gender, and race) will also be summarized.

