12.1.1. Incidence of Adverse Events

The following TEAE/SAE listings and summaries will be produced:

- overview of TEAEs
- summary of TEAEs by PT (all grade and grade \geq 3)
- summary of TEAEs by SOC and PT (all grade and grade \geq 3)
- summary of TEAEs by PT and maximum grade (1-5)
- list of SAEs
- summary of SAEs by SOC and PT (all grade and grade \geq 3).

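### Adverse event tables compare crude incidence over windows that only Arm 1's maintenance phase can extend, and they pool two Arm 1 regimens in one column

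*SAP*

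**What the plan says.** - **Objective.** Protocol 2.1.2 sets a between-arm safety comparison: "To compare the safety and tolerability of AM0010 in combination with FOLFOX versus FOLFOX alone".
- **Arm 2 duration.** SAP 6.4: "For ARM 2 (FOLFOX only) patients may receive FOLFOX for up to 12 cycles or 24 weeks". Protocol 2.2.1 puts the same limit on FOLFOX in both arms, and crossover is not allowed.
- **Arm 1 duration.** After FOLFOX ends, patients "may continue to receive maintenance pegilodecakin if the patient continues to receive clinical benefit" (SAP 6.4). Protocol 6.3.1 allows this after 12 cycles or earlier if FOLFOX is stopped for toxicity. Neither document sets a maximum number of maintenance cycles. Progression, toxicity, withdrawal and physician decision still end treatment.
- **AE window.** SAP 12.1 counts an event that "begins or worsens in grade after the date of first study drug administration through 30 days after all treatment discontinuation". Its next sentence also admits related serious events (SAEs) that start later, in either arm.
- **AE outputs.** SAP 12.1.1 to 12.1.3 list tables by preferred term, system organ class, grade, seriousness, relatedness and discontinuation. SAP 7.2 makes categorical summaries counts and percentages, and SAP 7.1 groups safety patients by treatment received. No person-time rate, time to first event, common cut-off or split by treatment period is planned for AEs.
- **Exposure outputs.** SAP 10.1.1 does make the split: cumulative dose, dose per cycle and relative dose intensity of AM0010 "will be summarized up to 12 cycle prior to maintenance period and repeated within the maintenance period".

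**The concern.** A crude percentage compares toxicity between arms fairly only if patients are at risk for similar lengths of time. Here the window follows the end of all treatment, and the design lets only one arm extend it. Part of any Arm 1 excess would then reflect longer observation, and that part would grow if AM0010 delays progression.

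Separately, the single Arm 1 column combines events on AM0010 plus FOLFOX with events on AM0010 alone, which SAP 10.1.1 describes as a different regimen: "After the 12 cycle, patient receiving benefit on ARM 1 can continue on maintenance cycle with double of the dose". From the planned tables a reader could not tell which regimen an event belongs to. At stake is the interpretation of a stated secondary objective. No safety hypothesis is tested.

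**Working it through.** **Plan figures reproduced.** The documents give no expected AE rate or treatment duration to reproduce. Their structural figures agree: 12 × 14 days = 168 days = 24 weeks. Ten AM0010 doses per 14 days at 0.4 or 0.8 mg give the 4 or 8 mg of SAP Table JZGB.10.1. Ten doses at 0.8 or 1.6 mg give the 8 or 16 mg that SAP 10.1.1 states for maintenance.

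**Inputs**
- Month = 30.4375 days (SAP 7.2). Cap c = 168/30.4375 = 5.52 months. Tail g = 30/30.4375 = 0.986 months.
- Median PFS as a proxy for time on treatment: FOLFOX 1.7 months overall and 3.0 months for ECOG 0–1 (Protocol 1.1.1); AM0010 plus FOLFOX in Phase 1b 2.6 months (Protocol 1.3.2).
- Assumptions: exponential time on treatment to progression, all eligible Arm 1 patients continue, no other stopping, and the same constant AE hazard h in both arms. The documents give no value for h; I use 0.1 per month and vary it.

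**Formulas**, with λ = ln 2 / median:
- Mean window, Arm 1 = 1/λ + g.
- Mean window, Arm 2 = (1 − e^(−λc))/λ + g.
- Crude incidence, Arm 1 = 1 − e^(−hg) · λ/(λ+h).
- Crude incidence, Arm 2 = 1 − e^(−hg) · [λ/(λ+h) · (1 − e^(−(λ+h)c)) + e^(−(λ+h)c)].

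**Example, 3.0 months in both arms.** 1/λ = 4.33 and e^(−λc) = 0.279, so about 79 of 283 patients per arm pass 24 weeks. Arm 1: 4.33 + 0.99 = 5.31 months. Arm 2: 4.33 × 0.721 + 0.99 = 4.10 months. Ratio 1.29.

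| Median, Arm 1 / Arm 2 (months) | Arm 1 on treatment at 24 weeks | Mean window, Arm 1 / Arm 2 (months) | Ratio | Incidence at h = 0.1, Arm 1 / Arm 2 | Difference, from unrounded values (points) |
|---|---|---|---|---|---|
| 1.7 / 1.7 | 10.5% | 3.44 / 3.18 | 1.08 | 27.2% / 26.2% | 1.1 |
| 2.6 / 3.0 | 23.0% | 4.74 / 4.10 | 1.15 | 34.1% / 32.4% | 1.7 |
| 2.6 / 2.6 | 23.0% | 4.74 / 3.88 | 1.22 | 34.1% / 30.8% | 3.3 |
| 3.0 / 3.0 | 27.9% | 5.31 / 4.10 | 1.29 | 36.8% / 32.4% | 4.4 |
| 4.07 / 3.0 | 39.0% | 6.85 / 4.10 | 1.67 | 42.9% / 32.4% | 10.5 |

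The last row applies a hazard ratio of 0.7375 (= 5.9/8) to time on treatment. That is the overall survival design value, borrowed only to show the direction; neither document states a PFS hazard ratio.

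**Varying h** at 3.0 months in both arms: 9.8% versus 7.8% at 0.02 per month; 87.6% versus 87.3% at 0.7 per month. The effect almost disappears for very frequent events.

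**What would cancel it.** The mean windows are equal if Arm 1 has an extra all-treatment stopping hazard δ = 1/3.12 − 0.231 = 0.090 per month, that is 1 − e^(−0.090 × 5.52) = 39% over 24 weeks. For medians of 2.6 to 4.0 months δ is 0.08 to 0.11 per month.

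**Check of a common cut.** Ending both windows at the earlier of 30 days after last dose and c + g gives each arm (1 − e^(−λc))/λ + g, so the ratio is 1.0 when time on treatment is equal. Ending Arm 1 at the start of maintenance instead removes its tail for the 27.9% who continue: 3.12 + 0.986 × 0.721 = 3.83 versus 4.10 months, and 30.8% versus 32.4% at h = 0.1. That reverses the bias.

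**The case against.** **The crude comparison can be defended.** Arm 1 is defined as the combination followed by optional maintenance, so whole-strategy incidence is a legitimate question, and over-counting in the experimental arm does not hide harm. This stands, and it is why the crude tables should stay.

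**Part of the gap is already covered.** Laboratory grades are given by cycle as well as at their worst (SAP 12.2), so thrombocytopenia and anemia can be compared within Cycles 1–12. Deaths are split by period (SAP 12.1.4). The number entering maintenance (SAP 8.1) and treatment duration (SAP 10.1.1) are reported, and late related SAEs count in both arms. This also stands and narrows the point. But reporting duration shows the imbalance without letting a reader correct each event for it, and non-laboratory AEs get no split.

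**Stronger readings that the documents do not support.** A reader might infer that the tables must be tilted against AM0010. The direction is only expected: it assumes treatment to progression and equal hazards on AM0010 alone and with FOLFOX, and much earlier stopping in Arm 1 would cancel or reverse it. Cycle delays (Protocol 5.3) could also lengthen Arm 2's window if 12 cycles run past 24 weeks. A reader might also take the 67% longer window as the size, but that rests on a borrowed survival hazard ratio, and the only AM0010 plus FOLFOX PFS median given, 2.6 months, is below the 3.0 months used for FOLFOX.

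**Conclusion.** The concern holds in limited form. The planned AE comparison is confounded with observation time, and one Arm 1 column pools two regimens. At the PFS medians the protocol cites, Arm 1's mean window is about 8% to 29% longer, worth roughly 1 to 4 percentage points for an event at 0.1 per month under the stated assumptions. It would be longer still if AM0010 delays progression. Less frequent and late events are affected most; overall TEAE incidence, if near its ceiling, hardly changes.

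Not modelled: Protocol 2.2.1 and 8.1.1 let some Arm 1 patients continue past initial progression while Arm 2 may not, which works in the same direction.

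The pooling of regimens does not depend on any of these assumptions. It would be wrong to conclude that the safety comparison is unusable; it lacks the supplementary tables needed to read it.

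**What to change.** In SAP 12.1:
1. Keep the crude whole-study tables.
2. Add exposure-adjusted incidence (patients with an event per patient-month at risk) for overall TEAEs, Grade 3 or higher TEAEs, SAEs and AEs of special interest. This is still needed beside the common cut, because time on treatment may differ between arms within 24 weeks.
3. Add a between-arm table with one identical rule: first dose to the earlier of 30 days after last dose or 24 weeks plus 30 days from first dose. Do not cut at the start of maintenance, since only Arm 1 can reach it.
4. Show Arm 1 maintenance-period TEAEs in a separate single-arm table, matching the split in SAP 10.1.1.

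The maintenance dose passages must also be reconciled so that this table can be labelled. Statements in the Protocol Synopsis, 2.2 (with Figure 4) and 5.1.3 (with Figure 7) give 0.4 or 0.8 mg. Other text in the Synopsis and 2.2, together with Protocol 5.1.1, 6.3.1 and SAP 6.3, gives 0.8 or 1.6 mg, with matching two-week totals in SAP 10.1.1.

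The cost is SAP wording and a few more tables from dates already collected. Trial conduct does not change; the downside is more output.

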12.1.1. Incidence of Adverse Events

The following TEAE/SAE listings and summaries will be produced:

- overview of TEAEs
- summary of TEAEs by PT (all grade and grade \geq 3)
- summary of TEAEs by SOC and PT (all grade and grade \geq 3)
- summary of TEAEs by PT and maximum grade (1-5)
- list of SAEs
- summary of SAEs by SOC and PT (all grade and grade \geq 3).

12.1.2. Relationship of Adverse Events to Study Drug

A TEAE will be considered as study drug related if the investigator considered the event as related to any study drug component. If the relationship to any study drug component is missing, this AE will be considered as study drug related AE.

The 4 summaries in Section 12.1.1 will be repeated for TEAEs/SAEs related to study treatment.

12.1.3. TEAEs Leading to Treatment Discontinuation

A summary table for TEAEs leading to any/each study drug component discontinuation will be presented by SOC and PT.

12.1.4. Death

A summary of death with the primary death reason and death period (all death, death during the treatment and within 30 days after treatment discontinuation, death >30 days of treatment discontinuation) will be presented based on ITT population.

12.1.5. Consolidated Adverse Event

Given the high level of granularity of the MedDRA dictionary, clinically identical or synonymous PTs reported under different terms in the database, in addition to being reported separately, will also be consolidated in a separate summary. The list of consolidated AE categories will be reported in the clinical study report.

12.1.6. Immune-Mediated Adverse Event

Potential immune mediated AEs, (eg, colitis, pneumonitis, endocrine, and hepatic events) will be summarized.

12.1.7. Adverse Events of Special Interest

Adverse events of special interest (AESIs) are AEs thought to be potentially associated with the study drug or the disease under study. Therefore, aggregate or single AE terms including additional medical interventions for identifying AEs possibly associated with the study drug were developed.

Adverse events of special interest are listed in the Investigator's Brochure. The MedDRA PTs that are grouped under each of the AESI terms will be provided.

12.2. Clinical Laboratory Evaluations

Hematology and chemistry laboratory values will be graded according to CTCAE v4.03. These calculated grades will be summarized by cycle and maximum post-baseline grade over the entire study. Shift tables from baseline to worst post-baseline CTCAE grade will be generated.

A listing of abnormal laboratory events will be presented.

12.3. Vital Sign Measurements

Blood pressure, heart rate, temperature, weight, BSA, along with changes from baseline will be summarized by scheduled visits.

12.4. Electrocardiogram

A twelve-lead electrocardiogram (ECG) including ventricular rate, PR, QRS, QT, and QTc intervals will be summarized. All numeric results along with changes from baseline will be summarized for all scheduled visits.

The QTc parameter will be summarized for the following categories:

• summarized by visit: QTc change from baseline 30 to <60 msec and ≥ 60 msec.

The patients with abnormal ECG will be listed.

12.5. ECOG Performance Status

Eastern Cooperative Oncology Group PS status will be summarized by visit.

All ECOG data will also be provided via a data listing.

12.6. Tumor Marker - CA 19-9

Patients with above normal CA19-9 at baseline will be included for the summary and percent change from baseline by visit using descriptive statistics for each treatment arm. The best change of CA19-9 from baseline is defined as the percentage change at the nadir from the baseline value, which will be summarized descriptively by treatment arm.

For patients with both baseline abnormal CA 19-9 and post-baseline assessments, the percent of patients with a maximum drop in CA19-9 of at least 20%, 50%, and return to normal will be calculated for each treatment arm.

12.7. Pregnancy

A listing of patients reporting a pregnancy during the treatment will be presented.

12.8. Utilization

Utilization data will be summarized by category across arms. The following categories will be described:

- transfusions (on study treatment and within 30 days after the treatment discontinuation)
- growth factor
- hospitalizations (on study treatment and within 30 days after the treatment discontinuation)
- post discontinuation systemic therapy

For categorical variables, frequency and the corresponding proportions will be summarized by treatment arm.

13. Pharmacokinetics

Pegilodecakin observed concentrations will be summarized by descriptive statistics.

Additional analysis utilizing the population PK approach may also be conducted if deemed appropriate. Relationships between pegilodecakin exposure and measures of efficacy and safety may be explored.

A separate analysis plan for pegilodecakin PK and exposure/response will be provided.

14. Immunogenicity

The treatment-emergent anti-drug antibody (TE ADA) evaluable population will be defined within the Safety Population as those patients with both a baseline ADA test result and a postbaseline ADA test result. As a proportion of the TE ADA evaluable population, the number and frequency of the following will be tabulated by treatment group: TE ADA+ patients, and TE ADA+ patients with detected higher-tier assay results. Included in the same tabulation will be, as a proportion of the TE ADA evaluable population, the number and frequency of patients with ADA present at baseline, as well as patients with detected higher-tier assay results at baseline.

A summary will be provided of the number and percentage of patients who receive pegilodecakin reporting specific TEAEs (overall and by PT) by patient TE ADA status (TE ADA+, TE ADA-, TE ADA Inconclusive, Patient not evaluable for TE ADA). The PT will be ordered by decreasing frequency in the TE ADA+ status group. The specific TEAE of interest are events in any one of the MedDRA Anaphylactic reactions Standardized MedDRA Query (SMQ), Hypersensitivity SMQ, Angioedema SMQ, Injection site reactions High Level Term (HLT), or Infusion site reactions HLT.

Additional immunogenicity analyses, to be presented in a standalone immunogenicity report in context with other studies of pegilodecakin, will be described in a separate SAP.

14.1. Interim Analysis

A planned first interim analysis will occur once at least 60 randomized patients who have the opportunity to receive 4 months of therapy from the date of randomization. The interim analysis is not designed to stop the study early for outstanding efficacy. Based on review of the PK exposure-safety and PK exposure-efficacy on the aggregated data of composite efficacy endpoints (PFS, ORR, and OS), the DMC will recommend continuing the Phase 3 trial, amending the study protocol, or stopping the study. The study will continue to enroll while this analysis is being completed.

A second interim analysis is planned when approximately 276 deaths (70%) of 393 deaths are reached in this event-driven trial. Details of the interim analysis results will be reviewed by the DMC. The DMC will inform the sponsor whether the interim efficacy boundary was met and provide the Sponsor with a recommendation to complete the trial as planned, modify, or discontinue the trial.

15. References

- Cox DR. Regression models and life-tables. J Royal Stat Soc Ser B. 1972;34(2):187-220.

Irwin JO. The standard error of an estimate of expectational life. J Hygiene. 1949;47;188-189.

- Karrison TG. Use of Irwin's restricted mean as an index for comparing survival in different treatment groups-- interpretation and power considerations. *Control Clin Trials*. 1997;18(2):151-167.

Leo Document ID = 1f124bc1-036e-4fe6-ab27-907d3eb67d37

Approver: PPD Approval Date & Time: 08-Apr-2019 00:38:08 GMT Signature meaning: Approved
